Study Title: Neural Facilitation of Movements in People With SCI
NCT number: NCT05354206
IRB ID #: 202111151 (The Washington University in St. Louis IRB)
PI: [name]
Document Type: Protocol
Document Date: 11/10/2022

Neural facilitation of stimulation-assisted movements in people with spinal cord injury

Principal Investigator:

[name]
Assistant Professor of Biomedical Engineering and Neurosurgery
Department of Biomedical Engineering
Washington University McKelvey School of Engineering
email: [contact]

Collaborators:

[name]
Instructor of Psychiatry
Department of Psychiatry
Washington University School of Medicine
email: [contact]

Study team members:

[name]
[name]
[name], OTD, OTR/L, ATP
[name]
[name], FNAI
[name]
[name]
[name], OTR/L, ATP
[name], PT, DPT, NCS

Version: November 10, 2022

Synopsis

Study title	Neural facilitation of stimulation-assisted movements in people with spinal cord injury
Objective	To understand the contribution of individual neural tracts to movements facilitated by transcutaneous spinal cord stimulation using transcranial magnetic stimulation, loud auditory stimuli, wearable sensors, motion tracking, and electromyography.
Hypothesis	Previous studies supported a potential role of spinal cord stimulation on the excitability of corticospinal and reticulospinal tract. We aim to identify the specific contributions of cortico- and reticulospinal networks towards reinforcing different types of movements enabled by transcutaneous spinal cord stimulation in unimpaired volunteers and volunteers with spinal cord injury. The results from this study may serve as preliminary data for the development of targeted rehabilitation strategies that take advantage of residual connections to maximize recovery after spinal cord injury.
Study period	Planned enrollment duration: approximately 12 months Planned study duration: 1-2 hours per subject, 5 visits
Number of subjects	112 (100 unimpaired, and 12 volunteers with spinal cord injury)
Study design	This study will measure changes in corticospinal and reticulospinal excitability associated with spinal cord stimulation during different leg movements.
Inclusion and exclusion criteria	
Inclusion Criteria:
 
Healthy volunteers
 
 1. Age between 18 and 65 years 2. Healthy people with no major comorbidities of any organ systems 
Exclusion Criteria:
 
 1. Subjects younger than 18 or older than 65 years 2. Subjects not providing consent or not able to consent 3. Subjects with any acute or chronic pain condition 4. Subjects with any acute or chronic disease of a major organ system 5. Use of analgesics earlier than 5 half-lives after the latest intake prior to study period 6. The use of caffeinated products within 3 hours prior to study period 7. History of epilepsy

8. Implanted metal
9. Active medical problems

SCI volunteers

1. Age between 18 and 65 years
2. Traumatic injury at the C4-T9 level, complete (ASIA A), or incomplete (ASIA B, C, or D)
3. At least one-year post injury
4. Stable medical condition
5. Difficulty independently performing leg movements in routine activities of daily living
6. Able to follow simple commands
7. Able to speak and respond to questions

Exclusion Criteria:

1. Subjects younger than 18 or older than 65 years
2. Subjects not providing consent or not able to consent
3. Subjects with any acute or chronic pain condition
4. Subjects with any acute or chronic disease of a major organ system
5. Use of analgesics earlier than 5 half-lives after the latest intake prior to study period
6. The use of caffeinated products within 3 hours prior to study period
7. Presence of tremors, spasms, and other significant involuntary movements
8. Etiology of SCI other than trauma
9. Concomitant neurologic disease, such as traumatic brain injury that will significantly impact the ability to follow through on study directions, multiple sclerosis, stroke, or peripheral neuropathy
10. History of significant medical illness including cardiovascular disease or insufficiency, uncontrolled diabetes, uncontrolled hypertension, osteoporosis, cancer, chronic obstructive pulmonary disease, severe asthma requiring hospitalization for treatment, renal insufficiency requiring dialysis, autonomic dysreflexia, etc.
11. Severe joint contractures disabling or restricting lower limb movements.
12. Unhealed fracture, contracture, pressure sore, urinary tract infection or other uncontrolled infections, other illnesses that

	
might interfere with lower extremity exercises or testing activities
 
 13. Depression, anxiety, or cognitive impairment 14. Deficit of visuo-spatial orientation 15. Sitting tolerance less than 1 hour 16. Severe hearing or visual deficiency 17. Miss more than 3 appointments without notification 18. Unable to comply with any of the procedures in the protocol 19. Botulinum toxin injection in lower extremity muscles in the prior six months 20. Any passive implants (osteosynthesis material, metallic plates or screws) below T9. 21. Any implanted stimulator in the body, e.g., pacemaker, vagus nerve stimulator, etc. 22. History of alcoholism or another drug abuse 23. Pregnancy (or possible pregnancy) 24. Having an Intrathecal Baclofen Therapy Pump (ITB pump) 25. History of epilepsy
Measurements	
Movement kinematics with video, muscle activity, motor evoked potentials by transcranial magnetic stimulation, and muscle responses after a loud auditory stimulus, before, during, and after transcutaneous spinal cord stimulation; depression and anxiety evaluation using the Beck Depression Inventory and Beck Anxiety Inventory questionnaires.

TABLE OF CONTENTS

1. Research aims	Pg. 6
2. Introduction	Pg. 7
3. Background and Significance	Pg. 7
4. Study Objectives	Pg. 8
5. Selection of Subjects – Inclusion/Exclusion Criteria	Pg. 8
6. Human Subjects	Pg. 10
7. Study Design & Methods	Pg. 12
8. Data Analysis and Statistical Plan	Pg. 16
9. Management of Intercurrent Events	Pg. 17
10. Data Safety and Monitoring Plan	Pg. 21
11. References	Pg. 22

1. Research aims

Electrical spinal cord stimulation (SCS) combined with exercise training has been shown to restore posture, stepping, and voluntary walking in humans with spinal cord injury (SCI). However, the neural basis of SCS induced recovery remains poorly understood, presenting significant barriers towards maximizing its use in rehabilitation. A better understanding of the specific improvements in motor function and potential for cortical and spinal plasticity could allow clinicians and physical therapists to personalize SCS mediated therapy according to individual needs. Additionally, allowing the brain to play an active role in the delivery of therapy could further enhance and accelerate the potential for recovery. In this study, we combine body-machine interfaces based on wireless wearable sensors with spinal cord stimulation to determine which kinds of SCS-facilitated movements are mediated by the corticospinal and reticulospinal tracts. We will evaluate corticospinal and reticulospinal tract excitability via transcranial magnetic stimulation (TMS) and loud auditory stimuli respectively. If successful, this study will allow us to study whether different types of training used in rehabilitation can be used to enhance the excitability of these neural structures and evaluate their role in the learning of skilled motor tasks. An understanding of how we can accelerate plasticity through residual cortical and reticulospinal connections may enable the development of rehabilitation strategies that take advantage of patient-specific residual functions to further augment recovery.

2. Introduction

Spinal cord injury (SCI) is a life-altering event that leads to long-lasting motor impairment, and currently, there is no 'cure' for paralysis¹⁻³. Through my work and that of others, electrical spinal cord stimulation (SCS) has been gaining momentum as a neuromodulation technique to re-enable movement of paralyzed areas⁴⁻⁶. Although regained movements below the injury have enabled activity-based interventions to induce unprecedented functional improvements in the chronic stage of paralysis⁷⁻¹⁰, the mechanisms of neurorecovery induced by electrical neuromodulation of the spinal cord remain poorly understood^{11,12}.

To better understand SCS-mediated neurorecovery, studies in rodent models of SCI using viral tracing¹³ and optogenetics¹⁴ suggest that corticospinal and reticulospinal projections mediate the voluntary control of paralyzed areas enabled by SCS, and activity-dependent reorganization of these circuits may be a primary contribution towards the restoration of function that has been observed in humans⁷⁻⁹. While direct recordings of these neural structures through viral tracing and optogenetics are not currently possible in humans, experimental paradigms exist to evaluate their involvement and contribution during SCS and motor tasks^{11,15}. Twenty minutes of SCS during rest has an excitatory effect at subcortical, but not cortical levels¹¹. However, it remains unclear whether this excitatory effect can be further enhanced by combining SCS with active voluntary movement. Indeed, despite the motor-enabling effects of SCS having been first observed half a century ago¹⁶, a major breakthrough in SCI research came from the combination of SCS with activity-based training^{4,5,7-9,17}. Moreover, while SCS can immediately enable a broad range of behaviors in animal models of paralysis^{13,18-20}, independent stepping without stimulation in humans has only been observed after more than a year of intense rehabilitation with SCS^{8,9,21}. In this work, we will evaluate corticospinal and reticulospinal tract excitability via transcranial magnetic stimulation (TMS) and reaction to a loud auditory stimuli (StartReact) respectively. Having a clear understanding of the neural mechanisms that are enhanced by SCS can allow the development of therapies that directly target the excitability and plasticity states of these structures towards improved and accelerated recovery.

3. Background and Significance

3.1 Rationale for this study

This 1-year study will provide the necessary data to prepare a clinical trial investigating whether activity-dependent reorganization of cortico- and reticulospinal circuits are primary contributors towards the long-lasting improvements in function that have been observed in humans. Moreover, we will study whether different types of training used in rehabilitation can be used to enhance the excitability of these neural structures and evaluate their role in the learning of skilled motor tasks²²⁻²⁵. An understanding of how we can accelerate plasticity through residual cortical and reticulospinal connections may enable the development of rehabilitation strategies that take advantage of patient-specific residual functions to further augment recovery.

4. Study Objectives

The goal of this project is to generate evidence-based knowledge of changes in the short-term excitability of corticospinal and reticulospinal neural structures that may mediate immediate improvements in motor function enabled by SCS.

Aim 1. Determine which kinds of SCS-facilitated movements are mediated by the corticospinal tract. I will use TMS to test whether SCS can enhance motor evoked potential (MEP) response time and amplitude as individuals use their legs to perform motor control tasks with different levels of dexterity.

Aim 2. Determine which kinds of SCS-facilitated movements are mediated by the reticulospinal tract. Using the same protocol, I will test whether SCS can enhance StartReact response time and amplitude.

5. Selection of Subjects – Inclusion/Exclusion Criteria

We plan to include in this study a total of 100 unimpaired and 12 SCI human volunteers over the course of one year.

Data collection will be performed at Washington University in St. Louis Danforth and Medical campus. Subjects will be referred by Drs. [name], [name], [name], [name], and [name], who are co-investigators on this project.

Approximately equal numbers of men and women will be recruited from all ethnic and racial groups. The racial composition of the population in St. Louis is approximately 44% Caucasian, 46% Black or African American, 4% Asian, 4% Hispanic, 2% Other. This will be the expected composition of our volunteer pool, of which the minority portion exceeds the national norm.

5.1 Healthy volunteers

Inclusion criteria

1. Age between 18 and 65 years
2. Healthy people with no major comorbidities of any organ systems

Exclusion criteria

1. Subjects younger than 18 or older than 65 years
2. Subjects not providing consent or not able to consent
3. Subjects with any acute or chronic pain condition
4. Subjects with any acute or chronic disease of a major organ system
5. Use of analgesics earlier than 5 half-lives after the latest intake prior to study period
6. The use of caffeinated products within 3 hours prior to study period
7. History of epilepsy
8. Implanted metal

9. Active medical problems

5.2 SCI volunteers

Inclusion criteria

1. Age between 18 and 65 years
2. Traumatic injury at the C4-T9 level, complete (ASIA A), or incomplete (ASIA B, C, or D)
3. At least one-year post injury
4. Stable medical condition
5. Difficulty independently performing leg movements in routine activities of daily living
6. Able to follow simple commands
7. Able to speak and respond to questions

Exclusion criteria

1. Subjects younger than 18 or older than 65 years
2. Subjects not providing consent or not able to consent
3. Subjects with any acute or chronic pain condition
4. Subjects with any acute or chronic disease of a major organ system
5. Use of analgesics earlier than 5 half-lives after the latest intake prior to study period
6. The use of caffeinated products within 3 hours prior to study period
7. Presence of tremors, spasms, and other significant involuntary movements
8. Etiology of SCI other than trauma
9. Concomitant neurologic disease, such as traumatic brain injury that will significantly impact the ability to follow through on study directions, multiple sclerosis, stroke, or peripheral neuropathy
10. History of significant medical illness including cardiovascular disease or insufficiency, uncontrolled diabetes, uncontrolled hypertension, osteoporosis, cancer, chronic obstructive pulmonary disease, severe asthma requiring hospitalization for treatment, renal insufficiency requiring dialysis, autonomic dysreflexia, etc.
11. Severe joint contractures disabling or restricting lower limb movements.
12. Unhealed fracture, contracture, pressure sore, urinary tract infection or other uncontrolled infections, other illnesses that might interfere with lower extremity exercises or testing activities
13. Depression, anxiety, or cognitive impairment
14. Deficit of visuo-spatial orientation
15. Sitting tolerance less than 1 hour
16. Severe hearing or visual deficiency
17. Miss more than 3 appointments without notification
18. Unable to comply with any of the procedures in the protocol
19. Botulinum toxin injection in lower extremity muscles in the prior six months
20. Any passive implants (osteosynthesis material, metallic plates or screws) below T9.
21. Any implanted stimulator in the body, e.g., pacemaker, vagus nerve stimulator, etc.
22. History of alcoholism or other drug abuse
23. Pregnancy (or possible pregnancy)

- 24. Having an Intrathecal Baclofen Therapy Pump (ITB pump)
- 25. History of epilepsy

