5.3 Withdrawal Criteria

1. Subjects will be allowed to withdraw from the study at any time upon request
2. Subjects' participation will be terminated if any of the inclusion criteria ceases to be valid or if any exclusion criteria will manifest after enrollment
3. Subjects' participation will be terminated if any significant depression is identified on the collected information on depression. Subjects will also be referred to a mental health professional.

Prior to scheduling, subjects will be screened over a phone interview to determine whether they meet the inclusion and exclusion criteria. All research personnel will have received training in the responsible conduct of human research as required by Washington University's Institutional Review Board (IRB).

6. Human Subjects Research

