7.1 Procedure Schedules – Full Protocol

SCI and Controls – Complete protocol

PROCEDURE	7.2 INITIAL EVALUATION			7.3 AIM 1	7.4 AIM 2
	Visit #1 Functional Mapping	Visit #2 Range of Motion	Visit #3 Familiarization	Visit #4 TMS	Visit #5 StartReact
Kinematic recordings					
EMG recordings					
Transcutaneous SCS					
BoMI					
Motor tasks					
TMS					
StartReact					

7.2 Initial evaluation: Determine the effect of SCS on motor responses and range of motion

To determine an initial baseline for each participant, we will evaluate motor responses elicited by transcutaneous SCS in the initial evaluation phase. Participants will visit the lab for 1) a functional mapping where we measure spinal responses elicited by SCS, 2) a range of motion evaluation where we measure the range of motion on different joints with and without SCS, and 3) a familiarization phase where participants learn to control the body-machine interface using their leg movements supported by SCS.

Participants: 100 unimpaired participants and 12 participants with spinal cord injury (spinal cord injury level C4-T9) with motor impairments in the legs (complete ASIA A, or incomplete ASIA B, C, or D) and in the chronic stage of SCI (>6 months postinjury) will participate in this experiment, which will be submitted for review and approval to Washington University School of Medicine Institutional Review Board. Unimpaired participants will be recruited to perform either one of the five potential visits (Visits# 1-5) or all five visits. Approximately 16 unimpaired participants are expected to complete each type of protocol. SCI participants will be recruited for the five visits in total.

Experiments with unimpaired, control participants will be used to refine collection procedures and instruments and to prepare an improved, more refined research design that will ensure effective and high-quality data collection with SCI participants. Data collected on control subjects will also be used to establish baseline behavior for comparison of SCI participant task performance and may be used to generate generalizable knowledge.

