Expected outcomes, potential problems, and alternative strategies: Based on previous studies by other groups, it is our expectation that MEP responses will be enhanced for the precision-control task in distal muscles (tibialis anterior), which are thought to require a high involvement from the corticospinal tract. *We hypothesize that SCS will further enhance the MEP response for these movements, but not for range-of-motion movements, or movements with proximal muscles (rectus femoris).*

The main challenge in this study will be the recruitment of a sufficiently large group of volunteers with spinal cord injuries in the C4-T9 level. If this will not be feasible, we will extend the study to individuals with lesions at the C2-C3 level that have complete or partial paralysis in the legs. Furthermore, we can seek to further extend the study to other hospitals in the St. Louis region like the Barnes Jewish Hospital, the Rehabilitation Institute of St. Louis, SSM Rehabilitation Hospital, and the VA Medical Center Spinal Cord Injury Program. Another potential difficulty may arise because of the high expected attrition with severely disabled volunteers. As a consequence, some evaluations might be interrupted. To preserve uniformity of statistical power across the study, we will retain the results of participants with an incomplete number of sessions in separate data sets. The analysis of incomplete data sets will take explicitly into account the causes for abandoning the study (e.g. dissatisfaction with the methodology, change in medical condition, etc).

Our approach will have –by design an objective—a degree of customization based on each individual’s specific mobility and potential for movement restoration with SCS. Therefore, there might be a small initial difference in performance. However, our previous studies have demonstrated an improvement in performance with training independent of differences in the BoMI map between subjects^{22,62,66,67}.

One possibility is that 45 minutes of BoMI training is not sufficient to observe changes in corticospinal and reticulospinal tract excitability within a single session. If this is the case, we will increase the duration of BoMI training to 2 hours. Twenty minutes to 2 hours of SCS and motor training have been shown to be sufficient to observe changes in motor function^{61,68,69} as well as spinal¹⁵, cortical²⁴, and subcortical¹¹ excitability in human subjects.

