8.4 Sample Size

We plan to include in this study a total of 100 unimpaired and 12 SCI human volunteers over the course of two years. We expect that only 90% of unimpaired and 70% of SCI subjects initially recruited will conclude the experiment. Therefore, we will need to recruit 110 unimpaired and 16 SCI volunteers in order to reach the recruitment targets.

The number of subjects has been powered from the results of previous studies using similar methods to investigate structural changes in the brain after BoMI practice^{22,73}. Although the power is adequate, it might be possible that we are unable to detect significant changes in motor capacity. If no within-subject significant changes are found in preliminary experiments, we can extend the duration of training within one session, or extend the protocol to several sessions. If no significant group changes are found, we can recruit six more SCI participants for the study (a 50% increase).

9. Management of Intercurrent Events

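### The SCI exclusion list has no rule on passive metal in the head, although every SCI participant is scheduled for cortical TMS and unimpaired volunteers are excluded for any implanted metal

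*Combined protocol and SAP*

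**What the plan says.** **SCI volunteers (section 5.2, repeated in the synopsis).** There are 25 exclusions, three of which name implants:
- Item 20: "Any passive implants (osteosynthesis material, metallic plates or screws) below T9".
- Item 21: implanted stimulators anywhere in the body.
- Item 24: an intrathecal baclofen pump.

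**Unimpaired volunteers (section 5.1, item 8).** The exclusion is "Implanted metal", with no limit on where in the body.

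**Exposure to TMS.** The Participants paragraph of section 7.2 states that "SCI participants will be recruited for the five visits in total". The schedule gives Visit 4 to TMS. Under Aim 1 in section 7, the target is the leg area of the motor cortex. If no motor threshold is found in a participant with SCI, full device output or the highest tolerable intensity is used. Unimpaired volunteers may do one visit or all five.

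**Screening and safety.** Section 5.3 says that before scheduling, "subjects will be screened over a phone interview to determine whether they meet the inclusion and exclusion criteria". Section 9.4 names the inclusion and exclusion criteria, together with monitoring, as the means of keeping risk minimal.

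**The concern.** The T9 limit in item 20 fits the site of the spinal stimulation, which is delivered over the lumbar spine. It does not fit the other stimulation in the study, which is delivered to the head. The SCI group, all of whom are scheduled for TMS, thus has no criterion on passive metal near the coil. The unimpaired group, not all of whom receive TMS, has a metal rule covering the whole body.

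Every SCI participant has a traumatic injury (inclusion 2, exclusion 8), so a past head injury repaired with metal is a conceivable history in this group. What is at stake is participant safety at Visit 4 and equal treatment of the two groups. Nothing in the estimation or testing depends on it.

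**Working it through.** No figure in the plan is in dispute, so the check is a comparison of texts, with some counting.

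**1. Does any SCI exclusion reach passive metal in the head?**
- Item 20 stops at T9 and covers only what lies below it.
- Item 21 would catch an active device in the head, but not a plate, clip or fragment.
- Item 24 concerns a pump.
- Item 9 mentions head injury, but as "traumatic brain injury that will significantly impact the ability to follow through on study directions". That is a test of function. Someone who has recovered well and carries a cranial plate passes it.
- Item 18 concerns inability to comply with study procedures and does not mention metal.
- Items 4, 10 and 12 concern disease, significant illness and conditions that interfere with testing. They could catch some of the same people on other grounds, but none turns on metal.

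Count: 3 of 25 items name implants; 0 of 25 cover passive metal in the head.

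**2. Does another written step close the gap?** The TMS safeguards in sections 9.3 and 9.4 are single pulses only, a gradual rise in intensity with feedback on comfort, and hearing protection. None is a check for metal.

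**3. Who is exposed?**
- SCI: all who follow the schedule. Section 8.4 gives a target of 12 and recruitment of 16. It adds that "we can recruit six more SCI participants for the study" if no significant group changes are found, which makes the target 12 + 6 = 18.
- Unimpaired: section 7.2 expects about 16 per type of protocol. If the types are the five single visits plus the full set (my reading), that is 6 × 16 = 96, close to the planned 100. TMS would then reach the Visit 4 group and the full-set group, 2 × 16 = 32. The rest would never receive it.

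**4. The rules side by side for one case.** Take a volunteer with a cranial plate and no other relevant history.
- Unimpaired: excluded by item 8 of section 5.1, even if enrolling only for a visit without TMS.
- SCI: passes all 25 items of section 5.2 and is scheduled for Visit 4.

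**5. What cannot be computed.** The documents give neither the frequency of cranial metal in this population nor a risk per exposed person, so no expected number of events can be derived.

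**The case against.** The strongest reply is that the documents never name passive metal as a TMS hazard. The implant-related entry in Table 1 of section 9.3 concerns induced currents in electrical circuits, and its examples are electrical devices. SCI items 21 and 24 address that class. Nor does the protocol tie the unimpaired metal rule to TMS: the rule applies to volunteers who will never have TMS and sits among broad criteria for good health. This stands. A reader might infer that the protocol recognises cranial metal as a TMS risk and then fails to act on it for SCI participants. The text does not support that reading.

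A second reply is that other routes would catch such a person. SCI subjects come by clinician referral or are identified through the electronic record (section 6.2). Section 9.3 conditions TMS safety on following guidelines. Investigators may discontinue anyone in that person's best interest. So it would be wrong to say that the phone interview is the only screen, or that staff would not ask about metal. But referral and record search work to the same recruitment criteria, and the guideline sentence sets no eligibility rule. Where the protocol does adopt a guideline measure for TMS, hearing protection, it writes it out. Discontinuation is discretionary and requires that someone already knows of the metal.

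A third reply is that item 18 could be stretched to cover a person who cannot undergo TMS. It could, but only if staff first decide that metal rules TMS out, and no rule says so.

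**Conclusion.** The point holds as an omission in the eligibility criteria. The SCI list restricts passive metal only below T9, leaves the head uncovered, and governs a group that is all scheduled for cortical TMS. The unimpaired list excludes any implanted metal. The case rests on two things in the documents: this unexplained difference between groups, and section 9.4's reliance on eligibility criteria for safety.

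Its size is limited. The list governs 12 targeted SCI participants (16 recruited, or a target of 18 under the extension), and the number with metal in the head may be zero. A reader might infer a measurable excess risk or a threat to the results. The documents support neither: no risk is quantified, and the analysis and power do not change. The change is worth making because it is cheap and bears on participant safety, not because harm has been shown to be likely.

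**What to change.** Keep item 20 as it is, for the spinal stimulation. Add one SCI exclusion to section 5.2 and to its synopsis copy: *Passive metal implants or fragments in the skull, brain or orbit (e.g., cranial plates, aneurysm clips), not including dental work.* Ask about it at screening. State that spinal fixation at the injury level remains allowed. This wording also serves if the study is extended to C2-C3 injuries, as the Aim 1 contingency text permits.

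**Cost.** One line in two places and one screening question. The downside is an occasional SCI screen failure, in a study that names SCI recruitment as its main challenge. The dental exception avoids needless failures.

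**Alternative not preferred.** A check before Visit 4, with only that visit omitted, would keep the person for the other visits. It would have to sit in the TMS procedure and not in the exclusion list, because section 5.3 ends participation "if any exclusion criteria will manifest after enrollment". Each person affected would cost one Aim 1 data set, 1/12 = 8.3% of the SCI target. The Aim 1 text would also set that person's data apart: "we will retain the results of participants with an incomplete number of sessions in separate data sets". A single exclusion at entry is simpler.
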